## **8.3 Recording of Adverse Events**

At each contact with the participant and their parent/guardian, adverse events will be assessed by specific questioning and, as appropriate, by examination. Information on all adverse events will be recorded immediately in the source document, and also in the appropriate adverse event form. All clearly related signs, symptoms, and abnormal diagnostic procedures results will be recorded in the source document, although they should be grouped under one diagnosis.

All adverse events occurring during the study period will be recorded. The clinical course of each event should be followed until resolution, stabilization, or until it has been determined that the study treatment or participation is not the cause. Serious adverse events that are still ongoing at the end of the study period must be followed up to determine the final outcome. Any serious adverse event that occurs after the study period and is considered to be possibly related to the study treatment or study participation will be recorded and reported immediately.

CONFIDENTIAL

This material is the property of the University of Minnesota. Do not disclose or use except as authorized in writing by the study sponsor

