## **8.5 Stopping Rules**

In the event that a participant has a serious adverse event that is deemed study-related by the lead-investigator for medical safety, the participant will be required to immediately withdraw from the study. The overall study may be stopped at any time at the request of the DSMB, principal investigator, and/or lead-investigator for medical safety. The main adverse effect that we expect to observe is excessive weight loss during the meal replacement period. In the context of this trial, we will define excessive weight loss as 2 consecutive weeks during which  $\geq 5$  pounds are lost per week for those with a BMI  $<40$  kg/m^2 and  $\geq 7$  pounds are lost per week for those with a BMI  $\geq 40$  kg/m^2. Individuals endorsing vomiting, laxative use, and/or diuretic use for weight control at the baseline visit will be excluded. We will also monitor for the incidence of disordered eating behaviors using the EDE-Q questionnaire, which will be administered at all in-person study visits. Any participant endorsing vomiting, laxative use, and/or diuretic use for weight control (via the EDE-Q) at any time during the trial will be interviewed using the Eating Disorders Module of the Structured Clinical Interview for DSM-5. If disordered eating is present upon clinical interview, the participant will be removed from the trial and referred to an eating behavior specialist for clinical follow-up. If no eating disorder is present, the participant may continue in the trial. The DSMB will be given the authority to stop the trial if the occurrence of excessive weight loss and/or incidence of disordered eating are deemed to be at an unacceptably high level. Participants will be instructed that they may withdraw from the study at any time and for any reason.

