#### **11.4 Potential Risks to Participants**

As with any research study, there may be unforeseen risks. A trained interdisciplinary research staff comprised of physicians, scientists, nurses, and study coordinators carefully guard against all potential risks.

Blood Sampling (fasting and during meal test)

There is minimal risk of bruising and infection associated with the blood draw.

Meal Replacements and Monitoring for Excessive Weight Loss and Disordered Eating Behaviors

Adverse events will be comprehensively documented at all study visits and during each monthly phone call. Participants will be instructed to contact study staff immediately if any adverse event is experienced. All participants will receive counseling regarding avoidance of unhealthy weight loss behaviors such as use of diuretics, diet pills, purging, or excessive exercise. However, this message will be delivered conscientiously so as not to provide participants with ideas they may not already have. We will serially assess multiple domains of unhealthy weight loss behaviors using the EDE-Q. The EDE-Q identifies disordered eating behaviors and unhealthy attitudes about weight such as purging, unhealthy obsession with dieting and/or body weight, prolonged fasting/starvation, use of laxatives to control weight, and excessive exercise. The EDE-Q has been validated and used extensively in the adolescent population and normative values and cut-points have been established for this age group. Participants will be asked to weigh themselves regularly, and monthly phone calls will be performed. We will use the in person visits to monitor for excessive weight loss defined as  $\geq 5$  pounds per week for those with a BMI  $< 40 \text{ kg/m}^2$  and  $\geq 7$  pounds per week for those with a BMI  $\geq 40 \text{ kg/m}^2$ . Participants reporting excessive weight loss will be given supplemental counseling regarding unhealthy weight loss behaviors and removed from the trial if excessive weight loss is noted for 2 consecutive visits.

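### Sections 8.5 and 11.4 define excessive weight loss differently, and no recorded weight can confirm the two-week event that 8.5 defines

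*Combined protocol and SAP*

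**What the plan says.** Section 8.5 (Stopping Rules) names excessive weight loss as the principal adverse effect anticipated. For this trial, "we will define excessive weight loss as 2 consecutive weeks during which" the loss is at least 5 lb per week (BMI below 40 kg/m²) or at least 7 lb per week (BMI 40 or above). The DSMB may stop the trial if it judges the occurrence unacceptably high. No numeric limit is given.

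Section 11.4 (Potential Risks to Participants) states: "We will use the in person visits to monitor for excessive weight loss defined as" the same two weekly rates, with no two-week requirement. It then sets two responses. The first is "Participants reporting excessive weight loss will be given supplemental counseling". The second is that the participant is "removed from the trial if excessive weight loss is noted for 2 consecutive visits".

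On weights between visits, 11.4 says only: "Participants will be asked to weigh themselves regularly, and monthly phone calls will be performed". It gives no frequency, scale, log or collection step. Table 1 schedules anthropometrics at baseline and weeks 8, 17, 26, 34, 43 and 52. The monthly contact in section 6.9 lists medical history, adverse events and counseling, but no weight.

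**The concern.** Staff have two rules for the same named event. One counts weeks and the other counts visits. Neither section refers to the other or says which governs, and 11.4 does not say how a weekly rate is obtained at a visit 8 or 9 weeks after the last one.

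The stake is safety monitoring. Participants are minors on 1,200 kcal per day, and one arm is paid $20 for each 0.5% of body weight lost. Two coordinators applying the text in good faith could record different events and reach different decisions on counseling or removal. The DSMB could then be judging a count whose meaning depends on which section was applied.

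**Working it through.** The plan states no event count or rate for excessive weight loss, so there is no figure of its own to reproduce. The check is arithmetic on the visit schedule.

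**Inputs.** Weekly thresholds are 5 lb (BMI below 40) and 7 lb (BMI 40 or above), from 8.5 and 11.4. Visits are at weeks 0, 8, 17, 26, 34, 43 and 52 (Table 1), so the gaps are 8, 9, 9, 8, 9 and 9 weeks. Follow-up visits have a ±7-day window (sections 6.3 to 6.8).

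**Smallest 8.5 event.** Threshold × 2 weeks: 5 × 2 = 10 lb, or 7 × 2 = 14 lb.

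**What 11.4 flags, by reading**

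| Reading of the 11.4 weekly rate | Loss needed for a flag, BMI below 40 | BMI 40 or above | Relative to the smallest 8.5 event |
|---|---|---|---|
| Any week the participant reports | 5 lb | 7 lb | 5/10 = 7/14 = 0.5 |
| The week just before a visit | 5 lb in that week | 7 lb in that week | 0.5, but only 6 of 52 weeks are examined |
| Average between clinic weights | 5 × 8 = 40 to 5 × 9 = 45 lb | 7 × 8 = 56 to 7 × 9 = 63 lb | 40/10 = 4.0 to 45/10 = 4.5 |

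With the visit windows, gaps run from 6 to 11 weeks. The averaged flag then runs from 5 × 6 = 30 to 5 × 11 = 55 lb, or 7 × 6 = 42 to 7 × 11 = 77 lb.

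**Can clinic weights show an 8.5 event?** Take the smallest event followed by stable weight. A 10 lb loss averages 10/8 = 1.25 or 10/9 = 1.11 lb per week, which is 25% or 22% of 5. A 14 lb loss averages 14/8 = 1.75 or 14/9 = 1.56 lb per week, again 25% or 22% of 7. The reverse also fails: weeks alternating between 10 lb and 0 lb lost average 5 lb per week with no two consecutive weeks at threshold. Clinic weights therefore neither confirm nor exclude the event.

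**Does an 8.5 event meet the 11.4 removal rule?** There are 51 pairs of consecutive study weeks. Five are split by a visit: (8,9), (17,18), (26,27), (34,35) and (43,44). The other 51 − 5 = 46 (90%, nominal visit times) lie inside one visit interval. An episode there can be noted at one visit at most, so it does not alone satisfy a two-visit rule on any of the three readings. This counts calendar positions. It is not a probability of harm or a share of participants.

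**Does 8.5 itself remove the participant?** It requires withdrawal for a study-related serious adverse event and, separately, for disordered eating confirmed at interview. It states no step for excessive weight loss as such.

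**The case against.** The strongest reply is that the two sections do different jobs. Section 8.5 defines a trial-level event for the DSMB. Section 11.4 sets a graded individual response: counseling on report, and removal if the loss persists to the next visit. Keeping a teenager in the trial after one short episode may be deliberate. That is a fair reading, and the 90% figure partly reflects what any two-visit persistence rule does. But the text does not say this. Both sections define the same term, and 8.5 gives no individual action for the event it defines.

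Detection also has real cover. At each contact, "adverse events will be assessed by specific questioning and, as appropriate, by examination" (section 8.3). In 11.4, "Adverse events will be comprehensively documented at all study visits and during each monthly phone call", and "Participants will be instructed to contact study staff immediately if any adverse event is experienced". The EDE-Q is given at every in-person visit, and section 7.3.3 tabulates recorded adverse events. A reader might infer that 8.5 events would go unnoticed; the documents do not support that. What stands is narrower: none of these safeguards supplies a weight against which a reported rate can be checked.

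A reader might also infer that 11.4 sets a threshold of 40 to 63 lb, or that it is as likely to be the looser rule as the stricter one. The text does not bear that out. It never mentions averaging, and its self-weighing request and reference to participants reporting the loss favor the reported-week reading. On that reading every 8.5 event also meets 11.4's weekly rate. The wording about in-person visits leaves the averaged reading possible, but it is the less natural one.

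Finally, the DSMB charter and the adverse event form are not among the documents and may settle the definition. Even so, a charter would not reconcile two protocol sections that site staff follow.

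**Conclusion.** The conflict is real and should be fixed. The definitions differ in duration and unit, an 8.5 event can be found only from participant report (including answers to adverse event questions), and it cannot be checked against a recorded weight. On the more natural reading, 11.4 flags at half the smallest 8.5 event; averaged between clinic weights, it flags at 4 to 4.5 times that event. On any of these readings, a single 8.5 event inside one visit interval does not alone meet the 11.4 removal rule, and 8.5 states no removal step for it unless it is a study-related serious adverse event.

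This rests on nominal visit times and on the protocol text alone. The documents give no expected frequency of the event, so no number of affected participants is claimed. Nor do they show that any DSMB count or removal decision has in fact varied. A reader might infer damage to the trial's main result; the primary analysis is not affected.

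**What to change.** 1. Use the 8.5 two-consecutive-week definition in both 8.5 and 11.4, for counting, counseling and individual action.
2. In 11.4, replace the request for regular self-weighing with weekly home weighing.
3. Record those weights at the existing 6.9 monthly contact.
4. State how the weekly rate is computed (for example, the difference between successive weekly weights, so that three weights establish one event) and which BMI, baseline or current, decides between 5 and 7 lb.
5. State what follows one event and what follows a repeat. The medical safety lead and the DSMB should choose the action.

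Clinic-interval weights can serve as a supplementary check using data already collected. They should not replace the weekly record, because they cannot see a short rapid loss that levels off before the next visit.

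**Cost.** An amendment to 6.9, 8.5 and 11.4 with IRB review, and one added field on the monthly-contact form. The weights would be self-reported. Weekly weights not recorded earlier cannot be recovered, so ascertainment would differ before and after the amendment, and DSMB reports should mark that date. If 11.4 is now applied to a single reported week, moving counseling to the two-week definition gives up that earlier prompt. The sponsor can keep it under a different name if it is wanted.

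### Only purging answers on the EDE-Q open the eating-disorder interview, and sections 8.5 and 11.4 give two different rules for excessive weight loss

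*Combined protocol and SAP*

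**What the plan says.** **Interview route.** Section 8.5 has the EDE-Q given at all in-person visits. "Any participant endorsing vomiting, laxative use, and/or diuretic use for weight control (via the EDE-Q) at any time during the trial will be interviewed" with the DSM-5 eating-disorders module. The consequence follows: "If disordered eating is present upon clinical interview, the participant will be removed from the trial and referred to an eating behavior specialist". A participant in whom the interview finds no eating disorder may stay in.

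**What the EDE-Q covers.** Section 11.4 says the instrument assesses several domains. Besides purging, it lists "unhealthy obsession with dieting and/or body weight, prolonged fasting/starvation, use of laxatives to control weight, and excessive exercise". It adds that cut-points exist for this age group, but gives none.

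**Weight rule in 8.5.** "we will define excessive weight loss as 2 consecutive weeks during which" the loss is at least 5 lb per week (BMI below 40) or 7 lb per week (BMI 40 or more). The only stated consequence is that the DSMB may stop the trial if such losses become too common.

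**Weight rule in 11.4.** "We will use the in person visits to monitor for excessive weight loss", at the same weekly rates but without the two-week condition. "Participants reporting excessive weight loss will be given supplemental counseling regarding unhealthy weight loss behaviors" and are "removed from the trial if excessive weight loss is noted for 2 consecutive visits". On weights between visits: "Participants will be asked to weigh themselves regularly, and monthly phone calls will be performed".

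**Context.** Table 1 puts visits at weeks 0, 8, 17, 26, 34, 43 and 52. The monthly contact in 6.9 covers health history, adverse events and counseling, and names no weight. Section 6.10.6 pays the incentive arm $20 for each full 0.5% below baseline weight, assessed at the six follow-up visits.

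**The concern.** Payment depends on the weight measured at a scheduled visit. Fasting or over-exercising before a weigh-in is therefore a plausible harm of the randomized component itself, in adolescents already prescribed 1,200 kcal per day. By the protocol's own account the EDE-Q collects this signal, yet the required individual response covers only purging. A participant could report fasting at every visit and keep receiving payments, with no interview or specialist referral required.

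One might expect the excessive-weight-loss rule to catch such a participant. It is stated in two different ways, and staff cannot tell which one governs or which weights to apply it to.

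**Working it through.** The plan states no figure on this point, so there is nothing to reproduce. The check sets the provisions side by side and then uses simple arithmetic on the visit schedule.

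**Step 1. From EDE-Q answer to required action.**

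| Answer on the EDE-Q | Said to be identified (11.4) | Interview required (8.5) | Specialist referral if confirmed (8.5) |
|---|---|---|---|
| Vomiting, laxatives, diuretics | Purging and laxatives named | Yes | Yes |
| Prolonged fasting or starvation | Yes | Not stated | Not stated |
| Excessive exercise | Yes | Not stated | Not stated |

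**Step 2. The two weight rules.**

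| | 8.5 | 11.4 |
|---|---|---|
| Rate | 5 or 7 lb per week | 5 or 7 lb per week |
| Duration | Two consecutive weeks | None for a first flag |
| Where judged | Not stated | In-person visits |
| Individual action | None | Counseling, then removal after two consecutive flagged visits |
| Interview or eating-specialist referral | None | None |

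Section 4.3.1 sends a participant who leaves the trial back to primary care, if applicable.

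**Step 3. Can clinic weights show the 8.5 pattern?**

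- Gaps between visits (Table 1): 8, 9, 9, 8, 9 and 9 weeks. With each follow-up visit allowed 7 days either side, a gap can run from 8 − 2 = 6 to 9 + 2 = 11 weeks.
- Smallest loss meeting 8.5: 2 × 5 = 10 lb, or 2 × 7 = 14 lb if BMI is 40 or more.
- If weight is otherwise steady, the average over the nominal gap is 10/9 = 1.11 to 10/8 = 1.25 lb per week, or 14/9 = 1.56 to 14/8 = 1.75 lb per week.
- Across the visit windows: 10/11 = 0.91 to 10/6 = 1.67, or 14/11 = 1.27 to 14/6 = 2.33 lb per week.

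All of these lie well below 5 and 7 lb per week. At the clinic, such a participant looks the same as one losing slowly and steadily. Two weights 8-9 weeks apart therefore cannot show a two-week pattern.

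**Step 4. Can home weights show it?** They could, if collected. Section 11.4 asks for self-weighing but sets no frequency and does not say whether those weights count. Section 6.9 names no weight to obtain.

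**Step 5. Does another provision close the gap?** Section 8.3 requires adverse event questioning at each contact and follow-up of events. Section 8.5 withdraws anyone with a study-related serious event. Section 8.6 calls for individual safety assessment, and 7.3.3 and 8.7 provide DSMB oversight. None of these links a fasting or exercise answer to an interview or a referral.

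**The case against.** The strongest reply is that the narrow trigger is a deliberate and consistent rule. It matches the baseline EDE-Q exclusion in 4.2 item for item, and purging is a clear yes-or-no signal. Under a 1,200 kcal diet, with activity counseling for everyone and 8-hour fasts before three visits, fasting and exercise answers are likely to be less specific. The EDE-Q items are not reproduced, so a usable item threshold cannot be checked from the documents. This stands as a reason to set a threshold and exclude the visit fast. It does not explain why these answers should have no stated consequence, and the protocol offers no rationale.

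The second reply is that individual safeguards are real. Section 11.4 counsels every participant against purging and excessive exercise. Adverse events are asked about at every contact, including the monthly one, and could bring rapid loss to light. The DSMB must include an eating-disorders specialist. Nothing forbids staff from following up a non-purging answer. All of this stands, so what is missing is a required individual response, not monitoring as such.

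A reader might also multiply out the 11.4 removal rule. Two consecutive intervals span 17-18 weeks, giving 5 × 17 to 5 × 18 = 85-90 lb, or 7 × 17 to 7 × 18 = 119-126 lb, and might conclude that the rule could hardly ever be met. That assumes the weekly rate is averaged between clinic visits, which 11.4 never says. The section speaks of participants reporting loss, just after asking them to weigh themselves. If one reported week counts at each of two visits, 2 × 5 = 10 lb or 2 × 7 = 14 lb would be enough. The spread shows that the wording is unclear. It does not measure a failure of the rule.

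**Conclusion.** The point holds as a low-cost safety improvement, in two parts. First, the required interview, and with it specialist referral, opens only on purging answers, although the protocol says the same questionnaire identifies fasting and excessive exercise. Second, 8.5 and 11.4 define and act on excessive weight loss differently. The 8.5 pattern (10 or 14 lb in two weeks) cannot be seen in weights taken 8-9 weeks apart, and the standing of home weights is not stated.

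A reader might infer that the comparison of disordered eating between arms is biased. The documents do not support this. Section 7.3.3 compares the incidence of disordered eating behaviors and is not limited to purging or to interview-confirmed cases, and no table of confirmed cases by arm is planned. That comparison needs no change, and no power or sample size figure is touched.

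The conclusion assumes that 11.4 describes the EDE-Q correctly and that the list in 8.5 is the complete interview trigger. How many participants would be affected cannot be derived from the documents, and no rate of disordered eating is assumed here. The DSMB charter is not among the documents and could contain further rules.

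**What to change.** **Section 8.5, interview trigger.** Add new prolonged fasting or starvation, or excessive exercise, for weight control, reported on the EDE-Q after baseline. Write the threshold into 8.5 in advance, or use plain endorsement, as for purging, if no item cut-point exists. Exclude the 8-hour fast required for visits. The same interview decides, and a participant without an eating disorder continues.

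**Sections 8.5, 11.4 and 6.9, weight rule.** Use one definition of excessive loss that can be checked with the weights collected. Ask for home weights at the monthly contact and at visits, and say that they count. State one path that sets out what leads to counseling, to interview and to removal.

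**Cost.** Short edits to three sections and a decision on the threshold, which the documents do not supply. No new instrument is needed, since the EDE-Q and the interview are already in use. The downside is some additional interviews, a share of which will find no disorder; their number cannot be derived from the documents. If the sponsor prefers to keep the narrow trigger, the two weight rules should still be reconciled.

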## **8.6 Medical Monitoring**

Safety monitoring will include individual participant comprehensive assessment and appropriate reporting of adverse events as they occur. Adverse events will be monitored closely and participants will be provided with information about the risks of the study intervention and provided with phone numbers to reach the principal investigator/study coordinator in case of emergencies.

CONFIDENTIAL

This material is the property of the University of Minnesota. Do not disclose or use except as authorized in writing by the study sponsor

## **8.7 Data and Safety Monitoring Board**

A DSMB will be established, which will include a pediatrician with obesity expertise, a pediatric psychologist or psychiatrist with eating disorders expertise, and a biostatistician. DSMB members will not be affiliated with the study. The DSMB will meet regularly (frequency to be determined by DSMB members) during the trial to review data and evaluate participant safety. A charter for the DSMB to outline the responsibilities and procedures for the conduct of the monitoring board will be developed and approved by its members along with a plan for frequency of data review prior to the commencement of the trial. Review materials for the DSMB will be prepared and presented by the study biostatistician. A report from each meeting will be sent to the principal investigator and co-investigators advising on the continuation of the study.

